	(4) Tumor recurrence rate (3 months ± 7 days after the end of the last treatment).
	(5) Incidence of adverse events (AEs) (3 months \pm 7 days after the end of the last
	treatment).
	(6) The incidence of Serious Adverse Events (SAEs) (3 months \pm 7 days after the end
	of the last treatment).
	(7) Incidence of device defects (after last treatment)
	Inclusion Criteria (Major Criteria):
	(1) $18 \leq age \leq 80$ years;
	(2) First-diagnosed patients with tumors of the nervous system, head and neck,
	chest, abdomen, spine, pelvic cavity, limbs, etc. by tissue/cell pathology;
	(3) ECOG physical condition is graded as 0 to 2;
	(4) Women of childbearing had negative results in the blood pregnancy test
	(Human Chorionic Gonadotropin, HCG) 7 days prior to the first treatment;
	(5) The subject or subject's guardian is able to understand the purpose of the
	study, demonstrate sufficient compliance with the protocol and sign informed
F1:_:L:1:4	consent form.
Eligibility	
criteria	Exclusion Criteria (Major Criteria):
	(1) The subject with radiotherapy contraindications, including the known genetic
	tendencies that increase the sensitivity of normal tissue radiotherapy or the
	accompanying diseases that lead to hypersensitivity to radiotherapy;
	(2) The subject with other uncontrolled tumors except that to be treated according
	to medical history or the investigator's estimation, or with other malignant tumors
	within five years prior to enrollment;
	(3) Implanted pacemakers or other metal prosthesis within the scope of proton
	therapy;
	(4) Other situations that investigator determines not suitable for enrollment.
Specifications	
for the use of	All subjects used the investigational medical devices Drade - from first and interest
investigational	All subjects used the investigational medical device: ProBeam for radiation therapy.
medical device	

Statistical analysis with SAS 9.4 software.

All data are described statistically, including baseline data, all efficacy measures, and all safety data. The measurement data give the mean, standard deviation, minimum, maximum, median, 25th quantile and 75th quantile; The counting data gives the frequency and composition ratio.

Effectiveness analysis

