3.1.4 Effectiveness evaluation methods

If it is not possible to follow up at the clinical trial center according to the visit arrangement due to the epidemic, the clinical examination can be examined by other tertiary hospitals, and the test results will be transmitted back to the clinical trial center for evaluation; The carrier of imaging data in the outer hospital is not limited, and it is necessary to ensure that the imaging department of the center can be opened and read.

3.1.4.1 The main effectiveness evaluation indicators and the methods and time selection of their evaluation, recording and analysis

(1) Tumor disease control rate (DCR).

Reason for selection: According to the clinical trial effectiveness evaluation in the "Guidelines for the Review of Clinical Evaluation Technologies of Proton Carbon Ion Therapy System" (CFDA Circular No. 4 [2018]): "In view of the local characteristics of radiotherapy, it is recommended that the efficacy evaluation should be based on local control, and according to the different diseases, the common standards in clinical research, such as the efficacy evaluation criteria for solid tumors, should be reasonably adopted RECIST. The efficacy evaluation can be divided into complete response CR, partial response PR, disease stable SD, disease progression PD, and the effective definition is: "CR+PR+SD." "; Due to the particularity of the disease, the evaluation method recommended in the relevant diagnosis and treatment guidelines is selected. The tumor disease

control rate was selected as the main effectiveness evaluation index, which was relatively objective and reproducible, and adopted the common standard in clinical research, which was widely recognized and applied by clinicians.

Definition of indicators: the occurrence of CR, PR and SD after the end of treatment is disease control; No biochemical recurrence at the end of prostate cancer treatment, no regional lymph nodes or distant metastases, considered disease control. Proportion of participants who developed disease control three months after the end of the last radiotherapy.

Metric type: Qualitative.

Data collection time: screening period, 3 months \pm 7 days after the end of the last treatment.

Evaluation time: 3 months \pm 7 days after the end of the last treatment.

Site of evaluation: Tumor receiving radiation therapy.

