Evaluation method: The changes in tumor CT or MRI imaging before and after treatment were evaluated by an independent imaging review panel according to RECIST 1.1. At 3 months of radiographic evaluation, if PD is found, PET-CT is required to confirm it.

Calculation formula: DCR = number of disease control subjects / total number of subjects × 100%.

Criteria: See RECIST 1.1 for details. At the time of 3-month imaging evaluation, if the patient is found to have PD, PET-CT examination is required to confirm it, if progress is confirmed, it is recorded as PD, if progress cannot be confirmed, it may be false progression, and it is recorded as SD. If prostate cancer does not have biochemical recurrence, PET-CT examination is not required, and there is no metastasis by default, which is regarded as tumor control, and if biochemical recurrence occurs, it is regarded as tumor not controlled, and PET-CT is required to confirm tumor metastasis.

Note: Participants who aborted the trial for any reason (except loss to follow-up) before the end of the last radiation therapy were considered to have disease progression (PD) or were not controlled. Disease site evaluation uses the same approach as baseline, including consistent contrasted/non-contrast scans and prompt scanning. If changes are needed, the case must be discussed with a radiologist to determine whether an alternative approach is possible. If not, the objective situation in the future is unclear.

3.1.4.2 Secondary effectiveness evaluation indicators and their methods and timing of evaluation, recording, analysis

(1) Objective response rate (ORR).

Reason for selection: The Guidelines for the Review of Clinical Evaluation Technologies of Proton Carbon Ion Therapy Systems (CFDA Circular No. 4 [2018]) recommends the use of the latest version of the commonly used evaluation criteria for radiation oncology as the clinical trial evaluation criteria, so RECIST 1.1 is used Relevant indicators as effectiveness evaluation criteria; Due to the particularity of the disease, the evaluation method recommended in the relevant diagnosis and treatment guidelines is selected. All of them can directly measure the effect of radiotherapy and are widely recognized and applied by clinicians.

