4.4 Expected shedding rate

In the sample size estimation process, the expected shedding rate is 10%.

This dropout rate refers to the proportion of participants who ultimately could not be included in the primary analysis. Shedding subjects are subjects who have been identified by the investigator as having serious protocol deviations. May include, but is not limited to, the following: the subject violates the inclusion criteria; Participants were not treated with experimental devices; Participants used concomitant medications/devices that are prohibited by the protocol; lack of data on key evaluation indicators; Participants did not obtain any data, etc.

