4.9 Selection criteria and rationale for participants included in the analysis

Full Analysis Set (FAS): All subjects who received at least 1 investigational device treatment and at least one post-baseline observation data will be enrolled in FAS, according to the basic principles of intention-to-heart analysis. FAS will be used as the primary population for baseline data and sensitivity analysis for validity evaluation. Participants may only be excluded in very limited circumstances, including when important inclusion criteria are violated and no observational data are available after enrollment.

Compliant protocol set (PPS): is a subset of FAS, defined as subjects who have measurable lesions at baseline and have completed at least one assessment of primary efficacy indicators after baseline. PPS will be the primary population for the effectiveness evaluation of this study.

Safety dataset (SS): all participants who received at least 1 study device treatment and at least one safety assessment. SS will be the primary population for safety analysis in this study.

The assessment of baseline characteristics will use the full set of analyses; The evaluation of effectiveness will use both the full analysis set and the conforming protocol set; Security analysis uses security datasets.

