congenital defects and other events.

Confidential Information Page 7 / 17

Statistical Analysis Plan Version: V1.0
Date: 2022-11-11

Calculation formula: incidence of serious adverse events = number of subjects with serious adverse

events in this group / number of all subjects in this group $\times 100\%$;

• Incidence of device defects

Device defects refer to the unreasonable risk that medical devices may endanger human health and life

safety under normal use during clinical trials, such as crashes.

Calculation formula: incidence of device defects = number of device defects / number of device use

 $\times 100\%;$

3 Statistical analysis set

The following analysis sets were defined in this trial for statistical analysis.

Full Analysis Set (FAS): According to the basic principles of intention-to-treat analysis, all participants who

received at least one treatment with an investigational device and at least one post-baseline observational data

will be included in the FAS. FAS will be used as the main population for the baseline data and effectiveness

evaluation sensitivity analysis of this study. Exclusion is only possible in very limited circumstances, including

cases where important enrollment criteria have been violated and no observational data have been available after

enrollment.

Per-Protocol Set (PPS): is a subset of FAS and refers to subjects with measurable lesions at baseline who

have completed at least one primary efficacy measure assessment after baseline. PPS will be the main population

in the evaluation of the effectiveness of this study.

Safety Set (SS): All participants who received at least one treatment with an investigational device and had

at least one safety evaluation. SS will be the primary population for safety analysis in this study.

The baseline characteristics will be assessed using the full analysis set, the effectiveness will be assessed

using both the full analysis set and the conformance set, and the safety analysis will use the safety dataset.

4 data processing

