5.6 Sensitivity analysis

If the receiver effectiveness index was filled by the worst observational data carry-over (WOCF) method,

the sensitivity analysis of the main effectiveness measure was performed based on FAS. When the conclusions

of FAS and PPS are consistent, the confidence of the test results can be enhanced. When the conclusions of the

two groups are inconsistent, the analysis based on the inclusion of PPS population should be the main one, and

the differences should be fully discussed and explained.

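### Prostate cancer is scored by a biochemical rule and listed entry needs no measurable lesion, yet the deciding per-protocol set admits only subjects with measurable lesions

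*Protocol*

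**What the plan says.** **Entry.** The only entry list in the documents is in the Protocol summary and is headed as major criteria. Criterion 2 admits "First-diagnosed patients with tumors of the nervous system, head and neck" and other sites, confirmed by pathology. The remaining criteria cover age, ECOG status, pregnancy test and consent. None mentions a measurable lesion.

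**Endpoint.** Protocol 3.1.4.1 scores control by RECIST 1.1, with a separate rule for one disease: "No biochemical recurrence at the end of prostate cancer treatment, no regional lymph nodes or distant metastases, considered disease control". Without biochemical recurrence, PET-CT is not needed and the subject counts as controlled. SAP 2.1.1 keeps the biochemical part of this rule. Both documents divide by the total number of subjects. The protocol names the irradiated tumour as the site of evaluation.

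**Analysis set.** Protocol 4.9 limits the PPS to those "defined as subjects who have measurable lesions at baseline" with at least one later primary assessment. In SAP 3 the PPS "is a subset of FAS and refers to subjects with measurable lesions at baseline who" have had such an assessment. Both call the PPS the main effectiveness population and give the FAS the sensitivity role.

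**Precedence.** Under SAP 5.6, if the conclusions of the "two groups are inconsistent, the analysis based on the inclusion of PPS population should be the main one".

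**Allowance.** Protocol 4.2.1 enlarges 42 to 47 for about 10% loss. Protocol 4.4 explains: "This dropout rate refers to the proportion of participants who ultimately could not be included in the primary analysis".

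**The concern.** The endpoint and the set on which it is decided do not cover the same people. The endpoint has a rule that can score a prostate subject without any lesion measurement. The PPS then removes that subject if no measurable lesion was present at baseline, although the subject met the listed entry criteria, followed the protocol and has a valid result. For such a subject the prostate rule never reaches the deciding analysis. The formula's denominator, all subjects, also does not match the PPS.

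The PPS wording does not say that the measurable lesion must lie in the irradiated tumour, which is where the endpoint is evaluated.

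The trial passes or fails on whether a lower confidence limit exceeds 80% in at most 47 subjects. A few subjects in or out can change that result. SAP 5.3.2 settles set membership at a data review meeting before lock. In an open single-arm study, the written definition should leave no room for choice at that meeting.

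**Working it through.** **Inputs.** Target 80% and expected 95% (Protocol 3.1.2); two-sided alpha 0.05 and power 80% (4.3); success if the 95% lower limit exceeds 80% (4.5); Clopper-Pearson limits (4.7.1); 42 evaluable and 47 enrolled (4.2.1).

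**1. The plan's own figure.** Normal approximation for one proportion:

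n = [(1.960 × √(0.80 × 0.20) + 0.8416 × √(0.95 × 0.05)) / 0.15]²
= [(0.7840 + 0.1834) / 0.15]² = 41.6, so 42.

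42 / 0.90 = 46.7, so 47. Both stated figures reproduce.

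**2. Exact power by PPS size.** For each n, find the smallest r for which the 2.5% quantile of Beta(r, n − r + 1) exceeds 0.80. Power is P(X ≥ r) for X binomial with n and 0.95.

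| PPS size | Controlled needed | Lower limit | Power |
|---|---|---|---|
| 47 | 44 | 82.5% | 79.3% |
| 46 | 43 | 82.1% | 80.3% |
| 45 | 42 | 81.7% | 81.3% |
| 42 | 39 | 80.5% | 84.3% |
| 41 | 38 | 80.1% | 85.3% |
| 40 | 38 | 83.1% | 67.7% |
| 37 | 35 | 81.8% | 71.8% |
| 34 | 32 | 80.3% | 75.9% |
| 33 | 32 | 84.2% | 50.4% |
| 26 | 25 | 80.4% | 62.4% |

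Power moves in a sawtooth because the rule is discrete. Every size from 41 to 46 exceeds 80%. Every size from 26 to 40 is below it, between 50.4% and 75.9%. Since 47 − 41 = 6, losses cost the stated power only when non-measurable subjects plus all other losses exceed 6.

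**3. Can the exclusion change the verdict?** Two hypothetical cases, with 47 in the FAS and no other losses:

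- FAS 43/47: lower limit 79.6%, fails. Remove 5 non-measurable subjects, 4 controlled and 1 not. PPS 39/42: lower limit 80.5%, passes.
- FAS 44/47: lower limit 82.5%, passes. Remove 7 non-measurable subjects, all controlled. PPS 37/40: lower limit 79.6%, fails.

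The verdict can move either way, and in both cases SAP 5.6 lets the PPS result stand. These cases show what is possible. They do not predict what will happen.

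**The case against.** Several points on the other side stand.

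- **The FAS is also analysed.** SAP 5.4.1 bases the primary evaluation on both sets, the FAS has no lesion restriction, and SAP 5.6 requires differences to be discussed. The excluded subjects therefore stay visible. But the PPS prevails in exactly the case where the choice matters.
- **The entry list may be incomplete.** Because it is headed as major criteria, a fuller list could require a measurable lesion. The prostate rule would then sit awkwardly with that list, and the passages would still need reconciling.
- **The number affected is unknown.** The documents give no prostate count and leave the meaning of measurable to RECIST 1.1. Pelvic tumours, one of five groups to be spread as evenly as possible, are not all prostate cancers.

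A reader might also draw stronger conclusions that the documents do not support:

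- *All prostate subjects are lost.* Some may have a measurable lesion.
- *The 42 is reached only if nobody lacks a measurable lesion.* It is reached whenever all losses total 5 or fewer.
- *The trial is underpowered because of this restriction.* Up to 6 losses do no harm, and at 47 with nobody excluded power is already 79.3%.
- *The 10% allowance leaves these subjects out.* Protocol 4.4 first defines the rate as everyone not in the primary analysis, and its list of examples is open-ended. It then describes such subjects as serious protocol deviations. That makes the section ambiguous, but it does not establish an omission.
- *Fully resected subjects are enrolled.* SAP 5.3.4 tabulates surgery as one of several kinds of treatment history, which does not show this.

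**Conclusion.** The inconsistency is in the text and needs no assumption about numbers. Followed as written, the plan removes from its deciding analysis any compliant prostate subject who has a valid month-3 outcome but no measurable lesion. It rests on the entry list as supplied and on at least one such subject being enrolled, which the criteria allow.

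The size of the effect is open. The number affected and the direction of any bias in DCR cannot be determined from the documents. The effect on power is conditional: at a true DCR of 95%, losses bring it below the stated 80% only if non-measurable subjects and all other losses together exceed 6 of 47. The case for a change is that it settles who counts in a pass/fail result. It does not depend on a demonstrated loss of power.

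**What to change.** Before database lock, reword the PPS in Protocol 4.9 and SAP 3 as FAS subjects who have a post-baseline primary assessment and either:

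- a measurable lesion in the irradiated tumour at baseline, or
- prostate cancer evaluable by the protocol's own biochemical rule.

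Report DCR in the RECIST-measurable subset as a supporting row. Let the DCR formula name the analysis set that supplies its denominator.

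The cost is wording in two definitions, a note to the formula and one table row. Treatment and data collection do not change. The downside is that the PPS then mixes two evaluation criteria, which the supporting row makes visible. Non-prostate subjects without a measurable lesion would remain in the FAS only, since the documents give no separate scoring rule for them.

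A new entry criterion is probably too late: the SAP is dated 2022-11-11, after the planned September 2022 end of short-term follow-up. Restating power at the PPS size obtained would not help either, because it leaves the definition as it is.

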Reason for selection: The Guidelines for the Review of Clinical Evaluation Technologies of Proton Carbon Ion Therapy Systems (CFDA Circular No. 4 [2018]) recommends the use of the latest version of the commonly used evaluation criteria for radiation oncology as the clinical trial evaluation criteria, so RECIST 1.1 is used Relevant indicators as effectiveness evaluation criteria; Due to the particularity of the disease, the evaluation method recommended in the relevant diagnosis and treatment

guidelines is selected. They are all commonly used indicators for the evaluation of tumor treatment effects, and are widely recognized and applied by clinicians.

Indicator definition: the time between the first assessment of the tumour as CR or PR and the time between the first assessment of PD or death from any cause.

Indicator type: quantitative.

Data collection time: 1 month \pm 7 days, 3 months, \pm 7 days after the end of the screening period, until tumor progression or subject death.

Evaluation time: 3 months \pm 7 days after the last treatment.

Site of evaluation: Tumor receiving radiation therapy.

Evaluation method: The changes in tumor CT or MRI imaging before and after treatment were evaluated by an independent imaging review panel according to RECIST 1.1. At 3 months of radiographic evaluation, if PD is found, PET-CT is required to confirm it.

Calculation formula: DOR = time to death from PD or any cause on the first assessment - time to CR or PR for the first assessment;

Criteria: See RECIST 1.1 for details. At the time of 3-month imaging evaluation, if the patient is found to have PD, PET-CT examination is required to confirm it, if progress is confirmed, it is recorded as PD, if progress cannot be confirmed, it may be false progression, and it is recorded as SD.

Note: If no tumor progression or death is observed during the follow-up period after the end of radiotherapy, the formula is: DOR > last visit time after the end of the last radiotherapy - CR or PR time for first assessment. Others are the same as ORR.

(3) Tumor disease control rate (DCR).

Reason for selection: DCR 3 months after the end of the last treatment was the primary evaluation index, and DCR at other follow-up time was used as a secondary evaluation index.

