2.1.2 Secondary effectiveness measures

• Objective response rate (ORR)

CR or PR was considered objective remission at the end of treatment, no biochemical recurrence

occurred at the end of prostate cancer at the end of treatment, and no regional lymph node metastasis or

distant metastasis was considered objective remission. Proportion of subjects with objective remission at

each time point after the end of the last treatment.

Calculation formula: ORR = number of subjects with objective remission / total number of subjects ×

100%

Time to Sustained Remission (DOR)

The time from the first assessment of the tumor as CR or PR to the first assessment of PD or death

from any cause.

Calculation formula: DOR = time to first assessment of PD or death from any cause - time to first

Confidential Information Page 5 / 17

Statistical Analysis Plan Version: V1.0
Date: 2022-11-11

assessment of CR or PR.

• Tumor disease control rate (DCR) at 1 month after the end of last treatment

The occurrence of CR, PR and SD after the end of treatment was considered to be disease control, and

the absence of biochemical recurrence at the end of treatment of prostate cancer was considered to be disease

control. Proportion of subjects with disease control 1 month after the end of the last treatment.

Calculation formula: DCR = number of subjects under disease control / total number of subjects ×

100%

Tumor markers (if required)

Tumor marker examination was performed and clinically significant changes in tumor markers (before

and after radiation therapy) were reported at the discretion of the investigator.

• Tumor-specific symptoms

Symptoms are recorded according to the type of disease, which may include, but are not limited to, the

following: pain, swallowing function, mobility, bleeding, visual acuity, appetite/weight, superficial lymph

node size, and clinically significant changes in reported symptoms (before and after radiation therapy) as

judged by the investigator.

• Ease of use (ProBeam System, Radiation Therapy Management Software (OIS), Radiation

Therapy Planning Software (Eclipse))

Investigators using the corresponding functions scored according to the Likert scale and collected open-

ended questions to evaluate the comprehensive feeling of ease of use during the treatment.

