5.4.2 Secondary effectiveness measures

Secondary effectiveness assessments were based on the full analysis set (FAS) and the permissible set (PPS).

• Objective response rate (ORR)

• Time to Sustained Remission (DOR)

Tumor disease control rate (DCR) at 1 month during follow-up period

• Tumor markers (if required)

Tumor-specific symptoms

• Ease of use (ProBeam System, Oncology Information System (OIS), Treatment Planning System

(Eclipse))

The 95% confidence interval was calculated by Clopper-Pearson for the above secondary efficacy indicators

of "objective response rate (ORR)" and "tumor disease control rate (DCR) during the follow-up period of 1

month".

For the "time to sustained response (DOR)" secondary efficacy measure, describe the sustained response.

Descriptive statistics were performed on the percentage of measurable tumor longest diameter sum (SLD)

from baseline, and a waterfall chart was made for the maximum percentage reduction of SLD in each subject

compared with the screening period.

For the secondary efficacy indicators of "tumor markers" and "tumor-specific symptoms", the changes

before and after are described, and the changes are described in the table.

For the secondary efficacy index of "product ease of use", the scores of each category and the total score

were calculated, and the details of the open questions were described in a table.

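### On the best-supported reading of the PPS entry rule, 1-month DCR and ORR in the PPS count only subjects who reach the 3-month assessment, which can bias both

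*Protocol*

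**What the plan says.** Protocol 4.9 admits to the PPS those FAS subjects who have measurable lesions at baseline and "have completed at least one assessment of primary efficacy indicators after baseline". SAP section 3 repeats the condition: "have completed at least one primary efficacy measure assessment after baseline". Protocol 4.9 adds that "PPS will be the primary population for the effectiveness evaluation of this study", and gives the FAS a sensitivity role for effectiveness.

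Protocol 3.1.4.1 defines the primary indicator as "Proportion of participants who developed disease control three months after the end of the last radiotherapy". Its data are collected at screening and at 3 months only. In 3.1.4.2 the protocol separates the time points: "DCR 3 months after the end of the last treatment was the primary evaluation index", while "DCR at other follow-up time was used as a secondary evaluation index".

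SAP 2.1.2 lists the 1-month DCR ("Proportion of subjects with disease control 1 month after the end of the last treatment") and the ORR as secondary measures. For the analysis sets, SAP 5.4.2 says "Secondary effectiveness assessments were based on the full analysis set (FAS) and the permissible set (PPS"; the permissible set is the translation's name for the PPS. Clopper-Pearson intervals are planned for both measures. SAP 4.3 fills missing ORR and DCR values by worst observation carried forward (WOCF).

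**The concern.** If PPS entry depends on the month-3 assessment, the 1-month analysis in that set conditions on the future. A subject scanned at month 1 who dies, progresses off study or withdraws before month 3 already has a month-1 outcome, yet that outcome is discarded. Leaving in this window may well be linked to how the tumour responded, so the remaining subjects need not represent those who were scanned.

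At stake is how early control and early response are described in the population that the protocol puts first for effectiveness. The trial's pass/fail decision is not affected.

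**Working it through.** **1. Which assessment opens the PPS?** Four statements, side by side:
- The primary indicator has one scheduled post-baseline time point, month 3 (protocol 3.1.4.1).
- DCR at any other time is classed as secondary (protocol 3.1.4.2), so a month-1 scan is not an assessment of the primary indicator.
- SAP 4.3 sees no need to fill primary data in the PPS, which fits a set of month-3 completers.
- Protocol 4.4 lists missing key evaluation data among the reasons for not being in the primary analysis.

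Together these make month-3 completion the best-supported condition. It is an inference, because neither definition names month 3.

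**2. Does another rule bring the subject back?** No. Withdrawal is scored as progression only before the end of radiotherapy (protocol 3.1.4.1), which does not cover months 1 to 3. WOCF fills a missing value for a subject in the set; it cannot restore a subject who is excluded from the set.

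**3. The plan's own numbers.** With target 0.80, expected rate 0.95 (protocol 3.1.2), two-sided alpha 0.05 and power 0.80:

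n = [(1.960 × √(0.80 × 0.20) + 0.8416 × √(0.95 × 0.05)) / 0.15]² = [(0.7840 + 0.1834) / 0.15]² = 41.6, so 42.

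42 / 0.90 = 46.7, so 47. The stated 42 and 47 reproduce, and the allowance is 47 − 42 = 5 subjects.

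**4. Direction.** Let N subjects be scanned at month 1, D of them progressors, and let L leave before month 3, k of them progressors. DCR among all scanned is 1 − D/N. DCR in the PPS is 1 − (D − k)/(N − L). The PPS figure is higher when k/L > D/N, equal when k/L = D/N, and lower when k/L < D/N.

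**5. Size, as an illustration.** The documents give no month-1 rates and no number of leavers. Assumptions: N = 47, all scanned at month 1 and all with measurable lesions; L at most 5.

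| Month-1 progressors | Who leaves | All scanned (95% lower limit) | PPS (95% lower limit) |
|---|---|---|---|
| 5 | 1 progressor | 42/47 = 89.4% (76.9%) | 42/46 = 91.3% (79.2%) |
| 5 | 3 progressors | 42/47 = 89.4% (76.9%) | 42/44 = 95.5% (84.5%) |
| 5 | 5 progressors | 42/47 = 89.4% (76.9%) | 42/42 = 100% (91.6%) |
| 5 | 5 controlled | 42/47 = 89.4% (76.9%) | 37/42 = 88.1% (74.4%) |
| 2 | 1 progressor | 45/47 = 95.7% (85.5%) | 45/46 = 97.8% (88.5%) |
| 2 | 2 progressors | 45/47 = 95.7% (85.5%) | 45/45 = 100% (92.1%) |

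The rows with 2 progressors are close to the plan's expected 95% control (0.05 × 47 = 2.35). Each progressor lost adds about 2 points. For ORR, an assumed 20/47 = 42.6% becomes 20/46 = 43.5% with one non-responder gone and 20/42 = 47.6% with five gone.

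**6. The other reading.** If a month-1 scan also qualifies for entry, nobody with a month-1 result is dropped for lack of a month-3 assessment, and the shift from this mechanism is zero.

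**The case against.** The strongest reply is that the month-3 condition is inferred. Both definitions ask for one or more assessments, an odd phrase for an indicator with a single time point. SAP 4.1 lets unscheduled data enter the WOCF analysis of the primary indicator, and SAP 5.7 summarises it over planned visits in the plural. The text is also a translation. This stands: the looser reading cannot be excluded, and it removes the month-1 problem. It creates a different one, since a subject with only a month-1 scan would enter the PPS with no month-3 outcome while SAP 4.3 says no filling is needed. Either way, the rule has to name its qualifying assessment.

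Second, the FAS version of both measures is already planned, with WOCF, and no target or hypothesis attaches to them. This also stands, and it limits the impact. It does not remove the point, because protocol 4.9 gives the FAS only a sensitivity role for effectiveness. The SAP 5.6 rule that the PPS prevails when the two sets disagree concerns the primary measure, so it neither helps nor harms here.

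Third, a reader might infer that the PPS 1-month results are necessarily too high, by as much as 11 points (89.4% to 100%). The documents do not support that. Nothing in them shows that month-1 progressors leave before month 3, and the direction can reverse. The 11-point case puts the whole 10% allowance between months 1 and 3, although protocol 4.4 counts eligibility violations, untreated subjects and prohibited treatments in that allowance. It also assumes that every leaver progressed and nobody else did.

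**Conclusion.** The point holds in a limited form. On the best-supported reading, 1-month DCR and ORR in the PPS depend on a later event, and no other rule in the plan undoes this. The result can be biased: upward if progressors or non-responders are over-represented among leavers, not at all on average if leaving is unrelated to the month-1 result, and downward if they are under-represented, for instance when all leavers were controlled. At the plan's expected 95% control, losing both of two month-1 progressors would move the DCR by about 4 points (95.7% to 100%). That is an illustration, not an estimate.

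The conclusion rests on reading the PPS rule as month-3 completion and on some subjects with a month-1 result leaving before month 3. It concerns secondary, descriptive measures that are also shown in the FAS. It is worth correcting, but it does not threaten the trial's primary conclusion.

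**What to change.** In SAP 5.4.2, make the FAS, with the planned WOCF, the lead analysis for 1-month DCR and 1-month ORR. If a restricted version is wanted, base it on FAS subjects who have a month-1 assessment, with measurable baseline lesions required for RECIST response, and not on the PPS. In protocol 4.9 and SAP section 3, name month 3 as the qualifying PPS assessment and limit the PPS to month-3 endpoints.

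The cost is a wording change in the two documents and a changed filter for two secondary tables. No new data are needed, and the FAS analysis is already planned. The downside for the sponsor is that the leading month-1 figures may become slightly less favourable.
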